#### **4.5.3.4 1-week IPG Stim On (Telephone Call #5)**

One week after IPG stimulation has been turned on, subjects will be contacted via telephone to query for pain intensity (BPI3), adverse events, medication usage, and details regarding the IPG charging pattern.

#### **4.5.3.5 2-Week IPG Stim On (Telephone Call#6)**

Subjects will be contacted via telephone again 2 weeks after the start of IPG stimulation to query for pain intensity (BPI3), adverse events, medication usage, and details regarding the IPG charging pattern.

#### **4.5.3.6 3-Week IPG Stim On (Visit 8)**

Following 3 weeks of IPG stimulation, subjects will return for evaluation of primary and secondary endpoints including the BPI, Pain Free Passive Range of Motion, SF-36v2, BDI-II, and the Patient Global Impression of Change scale.

Subjects will also be queried for medication usage and adverse events. To assess participant compliance with the stimulation regimen, [REDACTED]

[REDACTED] will be recorded in the subject records.

#### **4.5.3.7 6-Week IPG Stim On (Visit 9)**

Following 6 weeks of IPG stimulation, subjects will return for evaluation of the primary endpoint (the BPI) and to perform a safety check of the IPG and Implantable IM Lead sites and [REDACTED] of the SPR System. To assess participant compliance with the stimulation regimen, [REDACTED]

[REDACTED] will be recorded in the subject records.

Subjects will also be queried for medication usage and adverse events.

During this visit, the SULCS, and QST testing (optional) will be administered to subjects for which baseline SULCS and QST data are available.

#### **4.5.3.8 12-Week IPG Stim On (Visit 10)**

Following 12 weeks of IPG stimulation, subjects will return for evaluation of primary and secondary endpoints including the BPI, Pain Free Passive Range of Motion, SF-36v2, the BDI-II, the Patient Global Impression of Change scale, and a Subject Satisfaction Survey. Subjects will also be queried for medication usage and adverse events. To assess participant compliance with the stimulation regimen, [REDACTED] will be recorded in the subject records. The 12-week visit will serve as the primary efficacy analysis for the SPR System.

At the end of the visit, the number of daily hours of stimulation will be modified according to the pain relief reported by the subject:

- If the subject's BPI Question #3 score is  $\leq 2$ , the dosage (number of hours of stimulation per day) will be reduced from 6 hours to 4 hours.
- If the subject's BPI Question #3 score is greater than 2 but at least two points less than the baseline score (i.e., still reporting clinically significant pain relief), the dosage will remain at 6 hours per day.

- If the subject's BPI Question #3 score is not 2 points less than it was at baseline, the dosage will remain at 6 hours and the system will be checked for any technical problems.

#### **4.5.3.9 6-Month IPG Stim On (Visit 11)**

Following 6 months of IPG stimulation, subjects will return for evaluation of primary and secondary endpoints including the BPI, Pain Free Passive Range of Motion, SF-36v2, BDI-II, and the Patient Global Impression of Change scale. The SULCS and QST testing (optional) will be administered to subjects for which baseline SULCS and QST data are available. Subjects will also be queried for medication usage and adverse events. To assess participant compliance with the stimulation regimen, [REDACTED] will be recorded in the subject records.

At the end of the visit, the number of daily hours of stimulation will be modified according to the pain relief reported by the subject:

- [REDACTED] If the subject's BPI Question #3 score is  $\leq 2$ , the dosage [REDACTED]
- [REDACTED] If the subject's BPI Question #3 score is greater than 2 but at least two points less than the baseline score (i.e., still reporting clinically significant pain relief), the dosage [REDACTED]
- [REDACTED] If the subject's BPI Question #3 score is not 2 points less than it was at baseline, the dosage will [REDACTED]

#### **4.5.3.10 9-Month IPG Stim ON (Visit 12)**

Following 9 months of IPG stimulation, subjects will return for evaluation of primary and secondary endpoints including the BPI, Pain Free Passive Range of Motion, SF-36v2, BDI-II, and the Patient Global Impression of Change scale. Subjects will also be queried for medication usage and adverse events. To assess participant compliance with the stimulation regimen, [REDACTED] will be recorded in the subject records.

At the end of the visit, the number of daily hours of stimulation will be modified according to the pain relief reported by the subject:

- [REDACTED] If the subject's BPI Question #3 score is  $\leq 2$ , the dosage [REDACTED]
- [REDACTED] If the subject's BPI Question #3 score is greater than 2 but at least two points less than the baseline score (i.e., still reporting clinically significant pain relief), the dosage [REDACTED]
- [REDACTED] If the subject's BPI Question #3 score is not 2 points less than it was at baseline, the dosage [REDACTED]

#### **4.5.3.11 12-Month IPG Stim ON (Visit 13)**

Following 12 months of IPG stimulation, subjects will return for evaluation of primary and secondary endpoints including the BPI, Pain Free Passive Range of Motion, SF-36v2, BDI-II, the Patient Global Impression of Change scale, and a Subject Satisfaction Survey. The SULCS and QST testing (optional) will be administered to subjects for which baseline SULCS and QST data are available. Subjects will also be queried for medication usage and adverse events. To assess participant compliance with the stimulation regimen, [REDACTED]

[REDACTED] will be recorded in the subject records.

At the end of the visit, the number of daily hours of stimulation will be modified according to the pain relief reported by the subject:

[REDACTED] If the subject's BPI Question #3 score is  $\leq 2$ , the dosage [REDACTED]

[REDACTED] If the subject's BPI Question #3 score is greater than 2 but at least two points less than the baseline score (i.e., still reporting clinically significant pain relief), the dosage [REDACTED]

[REDACTED] If the subject's BPI Question #3 score is not 2 points less than it was at baseline, the dosage [REDACTED]

#### **4.5.3.12 Annual Long-Term Follow-Up Visits (Visits 14 and 15)**

Subjects will return to the clinic annually for long-term follow-up visits at 24-Months and 36-Months IPG Stim ON. During these visits, the BPI and Patient Global Impression of Change scale will be administered. Subjects will also be queried for medication usage and adverse events. To assess participant compliance with the stimulation regimen, [REDACTED]

[REDACTED] will be recorded in the subject records.

#### **4.5.3.13 Unscheduled Visits**

Subjects may need to return to the clinic for an unscheduled visit if they experience a technical issue with their SPR System or adverse event which requires further evaluation by the clinical study staff.

#### **4.5.3.14 Explant Follow-Up Visit**

Subjects requiring an explant of the SPR Implant Stage System (either the IPG, Implantable IM Lead, or both) will be required to return to the clinic for a 1-week follow-up visit after the explant procedure.

#### **4.5.3.15 Revision Surgery Visit(s) -If Applicable**

As noted in the risk section of this protocol, it is possible that subjects may require a revision surgery due to 1) migration of the implantable components resulting in loss of efficacy or subject discomfort, 2) failure of the implantable components, 3) rejection of the implantable components, 4) removal of the system due to a medical condition that requires MRI scanning, or 5) any other medical condition which necessitates removal of the system. If a revision surgery is necessary, the risks and any potential benefits of undergoing an additional surgical procedure will be discussed with the subject. Revision surgeries carry the same risks as the original implantation procedure and any additional subject specific risks will be discussed with the subject prior to any revision surgery. Additional visits to the clinic will also be necessary if a revision procedure is performed.

### **4.6 Study Visit Windows**

The acceptable windows for each visit and telephone call are listed in **Table 7**.

**Table 7.** Study Visit and Telephone Call Windows

Visit Number	Visit Name	Window
N/A	Trial Stage Consent Form	[REDACTED]
1	Baseline Visit	[REDACTED]
2	Trial Stage Procedure/Start of Sham	[REDACTED]
3	48-hour Safety Check	[REDACTED]
	Telephone Call #1	[REDACTED]
	Telephone Call #2	[REDACTED]
4	End of Sham/Turn ON Trial Stim	[REDACTED]
	Telephone Call #3	[REDACTED]
	Telephone Call #4	[REDACTED]
5	3-weeks Trial Stim ON/End of Trial Stage	[REDACTED]
Post-5	Trial Stage Follow-up Visit	[REDACTED]
	Telephone Calls #a-z	[REDACTED]
Pre-6	Implant Stage Eligibility/Consent	[REDACTED]
6	Implant Stage Procedure	[REDACTED]

7	1-Week Post-Implant / Turn IPG Stim ON	[REDACTED]
	Telephone Call #5	[REDACTED]
	Telephone Call #6	[REDACTED]
8	3-Weeks IPG Stim ON	[REDACTED]
9	6-Weeks IPG Stim ON	[REDACTED]
10	12-Weeks IPG Stim ON	[REDACTED]
11	6-Month IPG Stim ON	[REDACTED]
12	9-Month IPG Stim ON	[REDACTED]
13	12-Month IPG Stim ON	[REDACTED]
14	24-Month IPG Stim On	[REDACTED]
15	36-Month IPG Stim On	[REDACTED]

#### 4.7 Study Duration

The duration of the study is expected to be up to 10 years. The study will be conducted at up to five sites enrolling a total of 45 SPR Trial Stage subjects to yield approximately 18 subjects in the SPR Implant Stage. Study enrollment of 45 SPR Trial Stage subjects is expected to take approximately 7 years, and subject participation for those who progress to the SPR Implant Stage can last approximately 3 years.

#### 4.8 Early Termination

It is possible that this pilot study may be terminated prior to reaching 45 subjects participating in the SPR Trial Stage. Criteria for early termination of the study are detailed in Section 10.2.

#### 4.9 Subject Compensation

Subject compensation for participation in the study is presented in **Table 8**.

**Table 8.** SPR Subject Compensation Schedule

Visit Description	Visit or Call Number	Amount
Baseline	Visit 1	[REDACTED]
SPR Trial Stage Procedure/Start of Sham Period	Visit 2	[REDACTED]
48-hour Post-Lead Placement Safety Check	Visit 3	[REDACTED]
1-week Sham (Telephone Call #1)	Call #1	[REDACTED]
2-week Sham (Telephone Call #2)	Call #2	[REDACTED]
End of Sham Period/Turn Trial Stimulation ON	Visit 4	[REDACTED]
1-week Trial Stim On (Telephone Call #3)	Call #3	[REDACTED]
2-week Trial Stim On (Telephone Call #4)	Call #4	[REDACTED]
3-Week Trial Stim On/End of Trial Stage	Visit 5	[REDACTED]
Trial Stage Follow-up Visit	Visit Post-5	[REDACTED]
Trial Stage Follow-up Calls	Calls #a-z	[REDACTED]

Implant Stage Eligibility	Visit Pre-6	[REDACTED]
Implant Stage Procedure	Visit 6	[REDACTED]
1-week Implant Follow-Up/ Turn IPG Stim ON	Visit 7	[REDACTED]
1-week IPG Stim On (Telephone Call #5)	Call #5	[REDACTED]
2-Week IPG Stim On (Telephone Call#6)	Call #6	[REDACTED]
3-Week IPG Stim On	Visit 8	[REDACTED]
6-Week IPG Stim On	Visit 9	[REDACTED]
12-Week IPG Stim On	Visit 10	[REDACTED]
6-Month IPG Stim On	Visit 11	[REDACTED]
9-Month IPG Stim On	Visit 12	[REDACTED]
12-Month IPG Stim On	Visit 13	[REDACTED]
24-Month IPG Stim On	Visit 14	[REDACTED]
36-Month IPG Stim On	Visit 15	[REDACTED]
Unscheduled Visit (if applicable)- subjects who are asked to return to the clinic for an unscheduled visit will be compensated \$40.	No Visit Number	[REDACTED]
TOTAL		[REDACTED]

In addition to compensation for the study visits, when necessary, it is possible that transportation may be arranged for by the site on behalf of the study participant and covered by the study budget. Alternatively, subjects who are able to drive will receive reimbursement for mileage at the standard federal reimbursement rate.

## 5.0 DATA MANAGEMENT AND ANALYSIS

### 5.1 Data Collection

Baseline Case Report Forms (CRFs) will be completed for each subject who signs an informed consent. Subjects who sign an Informed Consent Form but do not receive a SPR Trial Stage System will not have any further data collected. The reason why the percutaneous lead was not placed will be documented in the subject's study file.

CRFs will be completed and maintained in a fashion that is consistent with accepted Good Clinical Practices used for Case Report Forms. CRFs will be completed in permanent blue or black ink and all entries will be made in a legible fashion. All fields will be completed unless, as stated above, the subject signed an Informed Consent, but did not elect to proceed in the study. If necessary, corrections will be made by using a single line strikeout with the initials and date of the person making the correction. The corrections will be made so as not to obscure the original data. Correction fluid or correction tape may not be used. Where specified, the Principal Investigator must sign and date the CRFs and questionnaires.

All CRFs will be stored in a locked storage facility (either a locked office or a locked cabinet).

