#### 4.2.2 Subject Disposition

Subject disposition in this study will be characterized as described in **Table 4** below.

**Table 4.** Subject Disposition Categories (continued on following page)

Disposition Category	Description
Screened Subjects	All subjects who are screened for potential study participation will be listed on a screening log. Those subjects who are excluded will be listed along with their reason for exclusion. Screened subjects include those individuals that were screened from record searches as well as those that came to the clinic, signed a consent form, and underwent further screening for eligibility.
Screen Failures (2 Levels)	
Any subject who signs an Informed Consent and does not receive a SPR Trial Stage System will be dispositioned as a screen failure as follows:
 
Level 1: Subjects who do not meet the pain intensity criteria (<math>\geq 4</math> on the baseline BPI3).
 
Level 2: Subjects who do not meet the criteria for the INR score or pregnancy test.
 
[REDACTED]

Enrolled	Subjects who sign a consent form AND meet all eligibility criteria will be assigned a study ID and will be considered “enrolled” at that time. Any subject who has a lead replaced will only be counted once against total study enrollment.
SPR Trial Stage Failure	Subjects who receive the SPR Trial Stage System but do not demonstrate at least a 2-point reduction on the BPI3 during the Trial Stage.
Withdrawn	Subjects who voluntarily withdraw their study participation or are lost to follow-up will be categorized as withdrawn.
Terminated	Subjects who are prematurely terminated from the study by the Investigator. Termination forms will capture the reason for study termination.
Completed	
Subjects who are Trial Stage successes and do not report a clinically significant and sustained return of pain within 6 months of the Trial Stage.
 
OR
 
Subjects who complete both the SPR Trial Stage and the Implant Stage and complete all follow-ups through the 36-month visit.

[figure not shown]

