#### **4.4.1.2 Safety**

The primary safety endpoint is the occurrence and type of device related adverse events (AEs). All AEs that occur during the study will be documented. Specific details regarding any observed AE will be collected on an AE Form and will be followed to resolution. The severity of each Adverse Event will be collected as well as its relationship to the SPR System. Any necessary treatment or intervention required and the resolution status of the adverse event will also be documented. AEs will be tabulated and summarized at the conclusion of the study. Additional details on the monitoring and adjudication of AEs is described in Section 11 (Data Safety Monitoring Board).

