#### **4.5.2.2 48-hour Post-Lead Placement Safety Check (Visit 3)**

In order to mitigate the potential risk of infection, subjects will return to the clinic for a check of the Lead exit site within 48 hours of the SPR Trial Stage procedure. The exit site will be examined for any signs of early infection. If any signs of infection are observed, the subject will be provided with appropriate treatment, including possible removal of the percutaneous lead. Please refer to details regarding the proper disposition of subjects who develop an infection in Section 4.2.2.1.

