#### 1) Risks associated with needle insertion for Smartpatch Lead placement

2) Risk of skin irritation, infection, or inflammation at the Smartpatch Lead exit site

[figure not shown]
3) Risk of the Smartpatch Lead breaking beneath the skin

4) Risk of infection associated with retained Smartpatch Lead fragments

5) Risks associated with lead fragment removal

[figure not shown]
6) Risk of Lead Replacement due to Lead Migration or Lead Becoming Dislodged

A large rectangular area of the page has been completely blacked out, indicating that the information has been redacted.

7) Risk of skin irritation under the Smartpatch Pad, Smartpatch Lead Connector Tape, or bandages

A large rectangular area of the page has been completely blacked out, indicating that the information has been redacted.

[figure not shown]
8) Risk of mechanical or electrical failure of the Smartpatch Stimulator

9) Risks for pregnant women

10) Risk of discomfort due to electrical stimulation

[REDACTED]

[REDACTED]

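### Section 5.1 ends data collection for consented subjects who receive no Trial Stage System, with no adverse-event exception; this contradicts 4.4.1.2, 5.4.2 and 7.4 and leaves failed lead placements unaccounted for in the primary safety endpoint

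*Combined protocol and SAP*

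**What the plan says.** Section 5.1 sets the rule: "Subjects who sign an Informed Consent Form but do not receive a SPR Trial Stage System will not have any further data collected". Two items are kept for these subjects. The first is baseline data: "Baseline Case Report Forms (CRFs) will be completed for each subject who signs an informed consent". The second is an explanation: "The reason why the percutaneous lead was not placed will be documented in the subject's study file". Later in 5.1 the group is described more narrowly, as cases where "the subject signed an Informed Consent, but did not elect to proceed in the study".

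Table 4 in section 4.2.2 gives the matching disposition: "Any subject who signs an Informed Consent and does not receive a SPR Trial Stage System will be dispositioned as a screen failure". The two visible screen-failure levels are the pain score, and the INR or pregnancy test. The same table counts a subject as enrolled once consent is signed and eligibility is met, which is before any placement.

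On adverse events, section 4.4.1.2 says: "All AEs that occur during the study will be documented". Sections 5.4.2 and 7.4 say the same in substance: every event is to be recorded and categorised, and events during the study go onto case report forms and are followed until resolved. None of the three is limited to subjects who received a system. The primary safety endpoint (synopsis and 4.4.1.2) is the occurrence of device-related adverse events.

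**The concern.** The cut-off in 5.1 is receipt of the system, not exposure to the placement procedure. A subject can be eligible, hold a study ID and undergo needle insertion at Visit 2, yet leave without a lead. Section 8.2.1 lists this exposure among the Trial Stage risks: "Risks associated with needle insertion for Smartpatch Lead placement". Section 3.1.1 lists the Introducer and the Smartpatch Test Needles as parts of the Trial System, so harm in an abandoned attempt can be device-related.

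A site that follows 5.1 would stop collecting data on that subject. A site that follows 4.4.1.2 would complete an adverse-event form. Sites could reasonably differ, and the analyst has no stated denominator to settle the matter. Complete counts matter beyond the final table: 6.1.1 has the DSMB chair review accumulating safety data for trends, and 7.4 treats anticipated device effects that occur more often than expected as unanticipated.

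**Working it through.** The plan states no figure on this point, so there is none to reproduce. The check is a comparison of text followed by an illustration of size.

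**1. Does the 5.1 rule reach a failed placement?** Its next sentence asks for the reason the lead was not placed, which fits an unsuccessful attempt as well as a change of mind. Table 4 applies to any consented subject without a system. The later phrase in 5.1 about not electing to proceed points to a narrower group. The plan does not define what it means to receive a system. The literal text reaches a failed placement; the intent is unclear.

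**2. What would be kept for such a subject?**
- Baseline forms and the reason for non-placement are kept. The reason goes to the study file, whereas 5.3 describes completed, monitored forms as what enters the database. A complication recorded only as a reason therefore has no stated route to analysis.
- Section 4.5.2.1 calls for procedure details at Visit 2.
- Section 4.5.2.2 says "subjects will return to the clinic for a check of the Lead exit site within 48 hours of the SPR Trial Stage procedure". That visit is timed from the procedure, but its purpose is to inspect the lead exit site, so whether it applies without a lead is unclear.
- The one-week visit in 4.5.2.9 is timed from lead removal, so without a lead it has no trigger.

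**3. Which events belong to the primary endpoint?**
- Events during an attempted placement can be device-related and so can belong to it.
- Events between consent and placement (a gap of up to 30 days under 4.5.1) precede contact with the device and would not ordinarily belong to it. For subjects who never receive a lead, losing these events conflicts with the all-events wording of 4.4.1.2 and 7.4. For subjects who do receive the system, the 5.1 rule does not apply.

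**4. How many subjects does the rule touch?** Table 3 gives about 90 subjects entered for eligibility and up to 45 undergoing the Trial Stage: 90 − 45 = about 45 without a system. The visible screen-failure criteria all come before device contact, so failed placements are probably a small part of these 45. Their number is not given.

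**5. Size, as an illustration.** Let x of 45 treated subjects have a device-related event, and add f subjects, each with a failed placement and an event. The proportion moves from x/45 to (x + f)/(45 + f). Neither x nor f is in the documents; both are assumed here. Intervals are exact (Clopper-Pearson) 95%.

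| x/45 | f = 1 | f = 3 | f = 5 |
|---|---|---|---|
| 0/45 = 0% (0 to 7.9%) | 1/46 = 2.2% (0.1 to 11.5%) | 3/48 = 6.3% (1.3 to 17.2%) | 5/50 = 10.0% (3.3 to 21.8%) |
| 5/45 = 11.1% (3.7 to 24.1%) | 6/46 = 13.0% (4.9 to 26.3%) | 8/48 = 16.7% (7.5 to 30.2%) | 10/50 = 20.0% (10.0 to 33.7%) |
| 10/45 = 22.2% (11.2 to 37.1%) | 11/46 = 23.9% (12.6 to 38.8%) | 13/48 = 27.1% (15.3 to 41.8%) | 15/50 = 30.0% (17.9 to 44.6%) |

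One omitted event moves the proportion by (x + 1)/46 − x/45 = (45 − x)/2070: 2.2 points at x = 0, 1.9 at x = 5 and 1.7 at x = 10. With f = 0 nothing changes.

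**6. Direction.** If e of the f failed attempts have an event, (x + e)/(45 + f) exceeds x/45 only when 45e > xf, that is, when e/f > x/45. Omission flatters the device only if failed attempts carry a higher event rate than treated subjects. The table assumes the extreme case, e = f.

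**The case against.** The strongest reply is that three sections already require every adverse event to be recorded, with no limit to treated subjects. Section 7.4 adds 24-hour reporting of unanticipated adverse device effects, which is also not tied to having a lead. On that view 5.1 is loose drafting aimed at people who never reached a procedure, as its own later phrase suggests. This stands to the extent that nothing is certain to be lost. It does not remove the conflict: 5.1 is a specific instruction to stop, the others are general statements, and the plan gives no order of precedence.

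A reader might infer that all data on these subjects cease. They do not: baseline forms and the reason for non-placement are kept. A reader might also infer that all scheduled safety checks lapse. That is not established for Visit 3, which is timed from the procedure.

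Redaction also limits the finding. Text after the second screen-failure level and much of the placement procedure are blacked out, and Table 5 has lost its layout. A further screen-failure level or a rule for failed attempts may exist there, so this point rests only on the visible, unqualified sentences in 5.1 and Table 4.

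Finally, this is a pilot case series in which events are tabulated and summarised, with no visible safety hypothesis. That bears on how serious the defect is, but does not excuse contradictory collection rules for the primary safety endpoint.

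**Conclusion.** The concern holds as an unresolved contradiction that should be corrected. Taken literally, 5.1 and Table 4 may leave device-related events from failed lead placements out of the primary safety endpoint, and may leave pre-placement events in never-treated subjects out of general adverse-event reporting.

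Three stronger conclusions might be drawn, and the documents do not support them:
- That these harms definitely drop out of the endpoint: 4.4.1.2, 5.4.2 and 7.4 say the opposite of 5.1.
- That the safety results are biased in the device's favour: this depends on failed attempts having a higher event rate than treated subjects, which is plausible where an attempt is abandoned because of a complication but is not shown.
- That the Implant Stage denominator has the same defect: the 5.1 rule concerns only subjects without a Trial Stage System, and every Implant Stage subject has had one.

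The size is unknown. If one event were omitted, the proportion would shift by about 2 percentage points on a base of 45, and an observed zero would become 2.2%. This assumes that 45 subjects are treated and that the omitted subject is additional to them.

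**What to change.** Amend the wording in three places.

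- **5.1 and Table 4:** confine the no-further-data rule and the screen-failure category to subjects in whom lead placement was never begun, and except adverse events from that rule. This brings both into line with 4.4.1.2, 5.4.2 and 7.4.
- **4.4.1.2 and 7.4:** state that adverse events are recorded from consent for every consented subject and followed to resolution as 7.4 already requires. Say how this follow-up is done when no lead is in place.
- **5.4.2:** define the Trial Stage safety population as every subject in whom lead placement was begun, and define when placement counts as begun. Report the number of attempts without a lead alongside the event table.

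The cost is an amendment and adverse-event forms for what are probably few subjects. The reported event rate may be slightly higher. Efficacy definitions are unaffected.
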